5.4.3 Immune-Related Adverse Events (IRAE's)

5.4.3.1 Definition of Immune-Related Adverse Events (IRAE's)

Blocking CTLA 4 or PD1 function may permit the emergence of auto-reactive T cells and resultant clinical autoimmunity. Rash/vitiligo, diarrhea/colitis, uveitis/episcleritis, hepatitis, and hypopituitarism were noted in previous ipilimumab studies. These drug-related events are presumptive autoimmune events, now termed IRAEs.

For the purposes of this study, an IRAE is defined as an AE of unknown etiology associated with drug exposure and consistent with an immune phenomenon. Efforts should be made to rule out neoplastic, infectious, metabolic, toxin or other etiologic causes prior to labeling an AE an IRAE. Serological, immunological, and histological (biopsy) data should be used to support the diagnosis of an immune-mediated toxicity. Suspected IRAEs must be documented on an AE case report form and as an SAE via CTEP-AERS (see Section [5.2](#)).

5.4.3.2 Monitoring and Treatment of Immune-Related Adverse Events (IRAE's)

Patients should be informed of and carefully monitored for evidence of clinically significant systemic IRAE (e.g., systemic lupus erythematosus-like diseases) or organ specific IRAE (e.g., rash, colitis, uveitis, hepatitis or thyroid disease). If an IRAE is noted, appropriate work-up (including biopsy if possible) should be performed, and steroid therapy may be considered if clinically necessary.

It is unknown if systemic corticosteroid therapy has an attenuating effect on ipilimumab activity. However, clinical anti-tumor responses have been maintained in patients treated with corticosteroids and discontinued from ipilimumab. If utilized, corticosteroid therapy should be individualized for each patient. Prior experience suggests that colitis manifested as \geq Grade 3 diarrhea, as well as other grade 3 IRAEs (skin rash, hepatitis, etc), requires corticosteroid treatment.

5.5 Treatment of Nivolumab Related Infusion Reactions

Since nivolumab contains only human immunoglobulin protein sequences, it is unlikely to be immunogenic and induce infusion or hypersensitivity reactions. However, if such a reaction were to occur, it might manifest with fever, chills, rigors, headache, rash, pruritus, arthralgias, hypotension, hypertension, bronchospasm, or other allergic-like reactions. All grade 3 and 4 infusion reactions that meet the definition of SAE in Section [5.2](#) must be reported via

Rev. 12/15
Rev. Add13

Rev. 11/16
Rev. Add13

CTEP-AERS according to the timeframes outlined in the AE table in Section [5.2.7](#).

Treatment recommendations are provided below and may be modified based on local treatment standards and guidelines, as appropriate:

- For **Grade 1** symptoms: (mild reaction; infusion interruption not indicated; intervention not indicated):
 - Study staff (e.g, RN, NP, PA or MD) should remain at bedside and monitor subject until recovery from symptoms. The following prophylactic premedications are recommended for future infusions: diphenhydramine 50 mg IV or PO (or equivalent) and/or acetaminophen/paracetamol 325 to 1000 mg at least 30 minutes before additional nivolumab administrations.
 - For **Grade 2** symptoms: (moderate reaction required therapy or infusion interruption but responds promptly to symptomatic treatment (e.g., antihistamines, non-steroidal anti-inflammatory drugs, narcotics, corticosteroids, bronchodilators, IV fluids); prophylactic medications indicated for ≤ 24 hours):
 - Stop the nivolumab infusion, begin an IV infusion of normal saline, and treat the subject with diphenhydramine 50 mg IV or PO (or equivalent) and/or acetaminophen/paracetamol 325 to 1000 mg; remain at bedside and monitor subject until resolution of symptoms. Corticosteroid and/or bronchodilator therapy may also be administered as appropriate. If the infusion is interrupted, then restart the infusion at 50% of the original infusion rate when symptoms resolve; if no further complications ensue after 30 minutes, the rate may be increased to 100% of the original infusion rate. Monitor subject closely. If symptoms recur, then no further nivolumab will be administered at that visit.
 - For future infusions, the following prophylactic premedications are recommended: diphenhydramine 50 mg IV or PO (or equivalent) and/or acetaminophen/paracetamol 325 to 1000 mg should be administered at least 30 minutes before nivolumab infusions. If necessary, corticosteroids (up to 25 mg of hydrocortisone or equivalent) may be used.
 - For patients experiencing infusion reactions to nivolumab administered over 30 or 60 minutes, subsequent infusions could be administered over 90 minutes.
- For **Grade 3 or 4** symptoms: (severe reaction, Grade 3: prolonged [ie, not rapidly responsive to symptomatic medication and/or brief interruption of infusion]; recurrence of symptoms following initial improvement; hospitalization indicated for other clinical sequelae (e.g., renal impairment, pulmonary infiltrates). Grade 4: Life-threatening; pressor or ventilatory support indicated):
 - Immediately discontinue infusion of nivolumab. Begin an IV infusion of normal saline and treat the subject as follows: Recommend bronchodilators, epinephrine 0.2 to 1 mg of a 1:1000 solution for subcutaneous administration or 0.1 to 0.25 mg of a 1:10,000 solution injected slowly for IV administration, and/or diphenhydramine 50 mg

Rev. Add14

Rev. Add14

IV or PO with methylprednisolone 100 mg IV (or equivalent), as needed. Subject should be monitored until the Investigator is comfortable that the symptoms will not recur. Nivolumab will be permanently discontinued. Investigators should follow their institutional guidelines for the treatment of anaphylaxis. Remain at bedside and monitor subject until recovery of the symptoms.

- In case of late-occurring hypersensitivity symptoms (e.g., appearance of a localized or generalized pruritus within 1 week after treatment), infusion reactions reported via CTEP-AERS should be graded according to NCI-CTCAE (Version 5.0) guidelines.

Rev. 11/16

5.6 Treatment of Ipilimumab Related Infusion Reactions

Since ipilimumab contains only human protein sequences, it is less likely that any allergic reaction will be seen in patients. However, it is possible that infusion of ipilimumab will induce a cytokine release syndrome that could be evidenced by fever, chills, rigors, rash, pruritus, hypotension, hypertension, bronchospasm, or other symptoms. No prophylactic pre-medication will be given unless indicated by previous experience in an individual patient. Reactions should be treated based upon the following recommendations.

- For mild symptoms (e.g., localized cutaneous reactions such as mild pruritus, flushing, rash):
 - Decrease the rate of infusion until recovery from symptoms, remain at bedside and monitor patient.
 - Complete the ipilimumab infusion at the initial planned rate.
 - Diphenhydramine 50 mg IV or PO may be administered at the discretion of the treating physician and patients may receive additional doses with close monitoring.
 - Premedication with diphenhydramine may be given at the discretion of the investigator for subsequent doses of ipilimumab.
- For moderate symptoms (any symptom not listed above [mild symptoms] or below [severe symptoms] such as generalized pruritus, flushing, rash, dyspnea, hypotension with systolic BP > 80 mmHg):
 - Interrupt ipilimumab.
 - Administer diphenhydramine 50 mg IV or PO.
 - Monitor patient closely until resolution of symptoms.
 - Corticosteroids may abrogate any beneficial immunologic effect, but may be administered at the discretion of the treating physician.
 - Resume ipilimumab infusion after recovery of symptoms.
 - At the discretion of the treating physician, ipilimumab infusion may be resumed at one half the initial infusion rate, then increased incrementally to the initial infusion rate.
 - If symptoms develop after resumption of the infusion, the infusion should be discontinued and no additional ipilimumab should be administered that day.
 - The next dose of ipilimumab will be administered at its next scheduled time and may be given with pre-medication (diphenhydramine and

acetaminophen) and careful monitoring, following the same treatment guidelines outlined above.

- At the discretion of the treating physician additional oral or IV antihistamine may be administered prior to dosing with ipilimumab.
- For severe symptoms (e.g., any reaction such as bronchospasm, generalized urticaria, systolic blood pressure < 80 mm Hg, or angioedema):
 - Immediately discontinue infusion of ipilimumab, and disconnect infusion tubing from the subject.
 - Consider bronchodilators, epinephrine 1 mg IV or subcutaneously, and/or diphenhydramine 50 mg IV or PO, with solumedrol 100 mg IV, as needed.
 - Patients should be monitored until the investigator is comfortable that the symptoms will not recur.
 - No further ipilimumab will be administered.
- In case of late-occurring hypersensitivity symptoms (e.g., appearance within one week after treatment of a localized or generalized pruritus), symptomatic treatment may be given (e.g., oral antihistamine, or corticosteroids).

Rev. 6/16
Rev. 11/16

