5.1.1 ARM A

5.1.1.1 Initial Treatment

Immunotherapy Induction: 1 cycle is 42 days (6 weeks) long.

Investigators can choose between two induction regimens (Regimen 1 or Regimen 2 below) of nivo/ipi which appear to have equivalent efficacy. (Lebbe C et al ESMO 2018)

Regimen 1: Nivolumab 1 mg/kg IV infusion Day 1 and 22 of Cycles 1 and 2.

Nivolumab is to be administered as a 30-60-minute IV infusion, using a volumetric pump with a 0.2 to 1.2 micron low-protein binding in-line filter at the protocol-specified dose. The drug can be diluted with 0.9% normal saline for delivery but the total drug concentration of the solution cannot be below 1 mg/mL. It is not to be administered as an IV push or bolus injection. At the end of the infusion, flush the line with a sufficient quantity of normal saline.

Ipilimumab 3 mg/kg IV infusion Day 1 and 22 of Cycles 1 and 2.

Ipilimumab is to be administered as a 30-90-minute IV infusion (dependent on institutional standard/policy), using a volumetric pump with a 0.2 to 1.2 micron low-protein

Rev. 6/16

Rev. Add14

Rev. Add16

binding in-line filter. Ipilimumab is given undiluted or further diluted in 0.9% NaCl Injection, USP or 5% Dextrose Injection, USP in concentrations between 1 mg/mL and 2 mg/mL.

Rev. Add14

Regimen 2: Nivolumab 3 mg/kg IV infusion Day 1 and 22 of Cycles 1 and 2.

Nivolumab is to be administered as a 30-60 minute IV infusion, using a volumetric pump with a 0.2 to 1.2 micron low-protein binding in-line filter at the protocol-specified dose. The drug can be diluted with 0.9% normal saline for delivery but the total drug concentration of the solution cannot be below 1 mg/mL. It is not to be administered as an IV push or bolus injection. At the end of the infusion, flush the line with a sufficient quantity of normal saline.

Rev. Add16

Ipilimumab 1 mg/kg IV infusion Day 1 and 22 of Cycles 1 and 2.

Ipilimumab is to be administered as a 30-90-minute IV infusion, using a volumetric pump with a 0.2 to 1.2 micron low-protein binding in-line filter. Ipilimumab is given undiluted or further diluted in 0.9% NaCl Injection, USP or 5% Dextrose Injection, USP in concentrations between 1 mg/mL and 2 mg/mL.

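### Section 5.6 suggests epinephrine 1 mg IV with no strength or rate; Section 5.5 gives 0.1 to 0.25 mg, diluted and slow, for an antibody infused on the same days

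*Combined protocol and SAP*

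**What the plan says.** Section 5.6 introduces its advice with "Reactions should be treated based upon the following recommendations". For severe symptoms it lists, as measures to consider when needed, bronchodilators, "epinephrine 1 mg IV or subcutaneously, and/or diphenhydramine 50 mg IV or PO", and an IV steroid. No epinephrine strength or speed of injection is given.

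Section 5.5 deals with Grade 3 or 4 nivolumab reactions and gives a separate instruction for each route. The intravenous instruction sets dose, strength and speed: "0.1 to 0.25 mg of a 1:10,000 solution injected slowly for IV administration". The alternative, by the other route, uses the stronger solution: "epinephrine 0.2 to 1 mg of a 1:1000 solution for subcutaneous administration". Section 5.5 adds "Investigators should follow their institutional guidelines for the treatment of anaphylaxis", and its lead-in says the recommendations "may be modified based on local treatment standards and guidelines, as appropriate". Section 5.6 has neither of these statements.

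The drugs share their induction days. In Regimen 1 of Section 5.1.1.1 the schedule is "Nivolumab 1 mg/kg IV infusion Day 1 and 22 of Cycles 1 and 2" and "Ipilimumab 3 mg/kg IV infusion Day 1 and 22 of Cycles 1 and 2". Regimen 2 changes the doses but not the days, and Section 5.1.4 repeats the schedule for Arm D. Nivolumab is preferably given first.

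**The concern.** The two sections print different IV doses of the same rescue drug for the same kind of emergency, and a patient on combined induction is exposed to both antibodies within one visit. If the causal drug is unclear, the treating team has two IV figures and no rule for choosing between them. The larger figure is also the less specified one: it has no concentration, no rate and no pointer to local anaphylaxis practice.

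This is a patient-safety matter. It does not touch the 2-year survival endpoint, the sample size or any analysis.

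**Working it through.** The plan has no calculated figure to reproduce here. The check compares the two texts route by route and then asks whether both can apply to one event.

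**Inputs**

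| Item | Section 5.5 (nivolumab, Grade 3 or 4) | Section 5.6 (ipilimumab, severe) |
|---|---|---|
| Epinephrine, IV | 0.1 to 0.25 mg of 1:10,000, slowly | 1 mg, strength and rate not stated |
| Epinephrine, subcutaneous | 0.2 to 1 mg of 1:1000 | 1 mg, strength not stated |
| Diphenhydramine | 50 mg IV or oral | 50 mg IV or oral |
| Steroid | 100 mg IV | 100 mg IV |
| Local modification allowed | yes | not stated |
| Institutional anaphylaxis guidelines | to be followed | not mentioned |

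**Step 1: IV dose ratio.** Dose in 5.6 divided by dose in 5.5: 1 / 0.25 = 4 at the upper end and 1 / 0.1 = 10 at the lower end.

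**Step 2: subcutaneous dose.** 0.2 ≤ 1 ≤ 1 mg, so the 5.6 figure is the top of the 5.5 range. There is no conflict.

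**Step 3: volume.** Ratio strengths are read as grams per millilitre, so 1:1000 is 1 mg/mL and 1:10,000 is 0.1 mg/mL.
- The 5.5 IV dose is 0.1 / 0.1 = 1 mL to 0.25 / 0.1 = 2.5 mL of 1:10,000.
- The 5.6 IV dose is 1 / 1 = 1 mL of 1:1000 or 1 / 0.1 = 10 mL of 1:10,000, and the text does not say which.

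**Step 4: overlap of schedules.** Ipilimumab days: 2 days × 2 cycles = 4. Nivolumab is scheduled on all 4, in both regimens and on Arms A and D. Maintenance is nivolumab alone, so the overlap is confined to induction.

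**Step 5: can one event fall under both sections?** A reaction during the first infusion belongs to that drug. A reaction during or after the second is less clear:
- The nivolumab risk list in Section 5.3.2 (footnote 7) places infusion reactions, including high-grade hypersensitivity, both during the infusion and straight after it. By then ipilimumab may be running.
- Sections 5.5 and 5.6 both recognise late hypersensitivity.
- Their descriptions share bronchospasm, low or high blood pressure, fever, chills, rigors, itching and rash, so the presentation may not identify the drug.

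**Step 6: does severity explain the larger figure?** It does not appear to. The smaller IV dose in 5.5 already covers Grade 4 reactions needing pressor or ventilatory support, while the severe examples in 5.6 include generalized urticaria.

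**The case against.** The strongest reply is that the sections concern different drugs and each is complete in itself. Nivolumab is preferably given first, with a line flush before ipilimumab, so a reaction during the ipilimumab infusion most naturally belongs to 5.6. That stands as the ordinary reading. It does not remove the overlap after the second infusion, though the overlap is an inference and no passage states it.

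Sections 5.1.1.1 and 5.4.2 also say that the combination is managed under the same guidance as nivolumab alone or under shared guidance, so a site could take 5.5 as governing. But neither names infusion reactions or withdraws 5.6, which is the more specific text, and the Appendix X algorithms do not include infusion reactions. If shared management is intended, the 5.6 line is the one out of step.

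The severity triggers differ (CTCAE grades in 5.5, clinical examples in 5.6), and neither section says whether its dose is per injection or a total. The ratio of 4 to 10 is therefore a comparison of printed figures, not of matched clinical situations.

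The wording in both places is advisory. Section 8.1.7 requires supervision by a physician experienced with IV agents, and Section 5.8 calls for optimal supportive care. All of that lowers the risk. Neither of those two sections supplies a dose.

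Finally, no harm is documented. Remaining ipilimumab exposure may be small: the drug is limited to Cycles 1 and 2, and Appendix XVI was already projecting sample numbers at completion of accrual in July 2020. That is a reasonable inference but is not established.

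**Conclusion.** The inconsistency is real and should be fixed. The IV epinephrine dose in Section 5.6 is 4 to 10 times that in Section 5.5, with no strength or rate, for two antibodies that share 4 of 4 scheduled ipilimumab days. The subcutaneous dose and the other rescue doses do not conflict.

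Confidence is high for the textual difference. That both sections can cover one event rests on the timing and symptom overlap in Step 5. The volumes rest on the usual reading of ratio strengths. The documents do not show which IV figure is clinically correct, and they give no severe-reaction rate and no count of patients still to receive ipilimumab, so clinical consequences cannot be sized. No statistical result changes.

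**What to change.** 1. Replace the epinephrine line in Section 5.6 with the route-specific instruction of Section 5.5 (dose, strength and rate for each route), or cross-refer to it, after the sponsor's clinicians and pharmacists have confirmed the figures.
2. If a different IV dose is intended for ipilimumab, state its concentration and rate and explain the difference from 5.5.
3. Add to 5.6 the instruction to follow institutional anaphylaxis guidelines.
4. State which section governs a reaction during or after the second infusion on a combined day.
5. Tell sites in a short memo.

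Item 1 alone removes the numerical conflict; items 3 and 4 close the remaining gap. The cost is a short protocol amendment and the memo, with no new procedures, patients or analyses.

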5.7 Prohibited and Restricted Therapies During the Study

Concomitant systemic or local anti-cancer medications or treatments are prohibited in this study while receiving ipilimumab/nivolumab and/or dabrafenib/trametinib treatments.

Patients may not use any of the following therapies during the study:

- Any non-study anti-cancer agent (investigational or non-investigational)
- Any other investigational agents
- Immunosuppressive agents (for Arms A and D).
- Physiologic replacement doses of corticosteroids are permitted if required
- Any non-oncology live vaccine therapies used for the prevention of infectious diseases (for up to 30 days prior to or after any dose of study drug)

NOTE: Patients are permitted to receive the seasonal influenza vaccine. If seasonal influenza vaccine is considered, killed vaccines should be recommended.

- Strong inhibitors or inducers of CYP3A4 or CYP2C8 (see [Appendix XI](#))

Rev. Add10

5.8 Supportive Care

All supportive measures consistent with optimal patient care will be given throughout the study.

Rev. 6/16
Rev. 11/16
Rev. 5/17

5.9 Quality of Life Studies

5.9.1 Patient Reported Outcome Measures: PRO-CTCAE, PROMIS, EQ-5D

Treatment-Related Symptoms & Toxicities: Due to a need for brief symptom-based PRO measures to assess unique side effects from ipilimumab + nivolumab and dabrafenib + trametinib with minimal participant burden, we propose administering items from the patient-reported outcomes version of the common terminology criteria for adverse events. (PRO-CTCAE)

Based on provider feedback, 12 PRO-CTCAE toxicities have been selected to reflect the full range of toxicities experienced by patients undergoing these two treatments. The items selected are: rash, headache, joint pain, decreased appetite, nausea, diarrhea, fatigue, cough, itching, abdominal pain, shortness of breath, swelling. PRO-CTCAE is not designed for comparisons and will be descriptive. We will report the number, frequency, and severity of toxicities if applicable.

Functional Domains: Functional areas that may show long-term deficits due to treatment will be assessed using the PROMIS® Profile-29. This standardized IRT-calibrated instrument contains the following measures: physical function, fatigue, pain interference, pain intensity, depression, anxiety, sleep disturbance, and social function. PROMIS item banks used to develop this profile have been extensively developed and tested.^{40, 41} PROMIS measures have exhibited strong construct validity when compared to existing PRO questionnaires in the domains of fatigue (FACT-Fatigue), pain (Brief Pain Inventory), sleep (Epworth Sleepiness Scale), and depression (CES-D).⁴²

Health Utility: The EQ-5D (5L) questionnaire will be used to elicit utility values from a societal perspective necessary for a quality adjusted time without symptoms of disease progression and toxicities of treatment (Q-TWiST) analysis. The EQ-5D (5L) brief preference-based health status measure, which contains 5 health attributes: mobility, self-care, usual activities, pain/discomfort, and anxiety/depression. Each attribute is measured by a question that has 5 possible responses: no problem, slight problem, moderate problem, severe problem, or unable/extreme problem. The combination of responses results in 125 (5⁵) possible health states. Prior research has developed a method for assigning a score between 0 and 1 to each across health states that represents an average US population preference for one state versus another.⁴³

Assessment schedule

Initial Treatment (Arms A, B)

- Baseline (at randomization or prior to the start of protocol treatment including Day 1 of cycle 1): PROMIS Profile-29, PRO-CTCAE, EQ-5D (5L)
- End of each treatment cycle (starting with cycle 1): PRO-CTCAE, EQ-5D (5L),
- End of first treatment cycle (6 weeks, can be measured on Day 1 of cycle 2): PRO-CTCAE, EQ-5D (5L), PROMIS Profile-29
- End of second treatment cycle (3 months, can be measured on Day 1 of cycle 3): PRO-CTCAE, EQ-5D (5L), PROMIS Profile-29
- Disease Stability (6 months; can be measured on Day 1 of cycle 5): PRO-CTCAE, EQ-5D (5L), PROMIS Profile-29

Long-Term Follow-up (for patients starting at least one dose of protocol treatment and not receiving any non-protocol therapy)

regardless of still receiving any protocol treatment (All study arms, indexed to study entry)

- EQ-5D (5L): every 3 months from study entry up to 2 years
- PROMIS Profile-29: at 6 weeks, 3 months and 6 months from study entry, then every 6 months up to 2 years

Ad-Hoc Assessments (End of Treatment in Each Step, Dose Modification)

- End of Step 1 Treatment (before crossover, for any reason including Section [5.9.2.2](#)): PROMIS Profile-29, PRO-CTCAE, EQ-5D (5L)
- End of Step 2 Treatment (after crossover, for any reason including Section [5.9.2.2](#)): PROMIS Profile-29, PRO-CTCAE, EQ-5D (5L)
- Dose Modification (Section [5.4](#)): PRO-CTCAE, EQ-5D (5L)

Second Treatment (Crossover, Arms C, D, indexed to second treatment)

- Baseline (at randomization or prior to the start of protocol treatment including Day 1 of cycle 1): PROMIS Profile-29, PRO-CTCAE, EQ-5D (5L)
- End of each treatment cycle (starting with cycle 1): PRO-CTCAE, EQ-5D (5L)
- End of first treatment cycle (6 weeks, can be measured on Day 1 of cycle 2): PRO-CTCAE, EQ-5D (5L), PROMIS Profile-29
- End of second treatment cycle (3 months, can be measured on Day 1 of cycle 3): PRO-CTCAE, EQ-5D (5L), PROMIS Profile-29
- Disease Stability (6 months; can be measured on Day 1 of cycle 5): PRO-CTCAE, EQ-5D (5L), PROMIS Profile-29

Assessments

We will conduct PRO assessments in regular, clinically informative intervals to evaluate short-term and long-term toxicities and functional impact for each treatment. We will assess all PROs at study randomization to provide the overall baseline scores to evaluate change across initial treatment, and long-term follow-up. We will evaluate treatment sequence by using the overall baseline assessment at randomization for treatment 1 and the initiation of treatment 2 (after progression and washout period) for baseline assessments.

During initial and secondary treatment periods, we will measure patient-reported toxicities (PRO-CTCAE) and overall health (EQ-5D (5L)) at each clinical visit where adverse events (CTCAE) are evaluated. Broader measures of physical and mental function (PROMIS Profile-29) will be collected at important clinical points: at six weeks (end of cycle 1), three months (end of second cycle), and 6 months (disease stability).

We will conduct all long term follow-up assessments (regardless of still on study treatment given no non-protocol treatment has been

administered) indexed to study entry every 3 months up to 2 years. EQ-5D (5L) assessments will be collected more frequently to coincide with the adverse events assessment (by CTCAE, every 3 months) until year 2. These additional assessments will be used to provide toxicity severity informing our primary 2-year PRO endpoint.

Throughout the study period we will conduct additional ad-hoc assessments for the following situations that may occur: end of treatment in each step (before crossover and after crossover). We will administer PRO-CTCAE and EQ-5D (5L) at the start of all dose modifications (Section [5.3](#)).

End of step 1 treatment and subsequent enrollment into step 2 treatment will trigger two assessments. One at the point end of step 1 treatment is documented, and a separate assessment at the initiation of secondary treatment after washout (treatment 2 baseline). Assessments will also be administered at the point end of step 2 treatment (after crossover) occurring within our follow-up window.

We acknowledge that post-crossover assessments must be interpreted cautiously given that participants will crossover at different times and may have residual symptoms from the first treatment, despite washout. However, these assessments will allow us to identify an optimal sequence of the 2 therapies from the patient's perspective. Following crossover, PROMIS Profile-29, PRO-CTCAE, EQ-5D (5L) will be administered following the same procedure as the initial treatment to month-6 allowing comparisons by treatment sequence.

Rev. Add10

Rev. 5/17

Rev. 5/17,
10/17

5.9.2

Patient Reported Outcome Measures: Tobacco Use Assessment

